## 2. Secondary Analysis

As a secondary analysis [IR-5], we will repeat the primary analysis using a distributed-analytic method that only requires sharing of summary-level information. The only difference is we will analyze percent weight changes (from baseline) at 1, 3, and 5 years separately as the analytic tools to fit mixed effects models in distributed databases do not exist yet. Specifically, we will use the distributed linear regression method to compare percent weight changes at 1 year (or 3 or 5 years) between surgery groups. We will consider either PS regression or PS matching as they allow us to use the distributed linear regression approach to conduct analysis using aggregate-level information only. In distributed linear regression, the parameter estimates and covariance matrix have a closed form solution and can be calculated by combining intermediate, summary-level statistics from all sites.

The importance of the secondary analysis is two-fold. First, it will allow us to include additional sites that are not able to share their patient-level data for the primary analysis, thereby allowing us to examine the robustness of our results in a much larger sample size. Second, this will be a key infrastructure activity as it will assess the feasibility and validity of using summary-level information to perform the same analysis that is conventionally done with pooled patient-level information. If proven feasible for PCORnet, the analytic method can further enhance the functionalities of the system by allowing sites to share less sensitive information while preserving the scientific rigor of the study.

There is strong evidence of a temporal trend in the use of the bariatric procedures, and the characteristics of patients who undergo these procedures may also change over time. As a sensitivity analysis [IR-5], we will look at the effects of these procedures on BMI changes by calendar year.

## B. AIM 2 (IMPROVEMENTS IN DIABETES RISK)

### 1. Primary analysis

The analytic framework for Aim 2 is similar to that described in Aim 1. The primary analysis will have three pairwise comparisons. The primary outcome of interest is: (1) remission from diabetes (a time-to-event outcome), defined as HbA1c <6.5% after 90+ days of not having any active anti-hyperglycemic prescription order or dispensing post-surgery. We will estimate the PSs as described in Aim 1, and fit a Cox proportional hazards model to estimate the effects of surgery on diabetes remission, with a maximum follow-up of 1, 3, or 5 years after surgery [CI-3]. In addition to regression, matching, and weighting considered in Aim 2, PS stratification is also compatible with Cox regression. Specifically, we can fit a stratified Cox regression stratifying on site and site-specific PS percentiles (e.g., deciles). The secondary outcome of interest is the differential impact of the procedures on glycemic control, measured as change in HbA1c from baseline to 1, 3, and 5 years. As this secondary outcome is a continuous variable, our analytic approach will be similar to the one described in Aim 1.

Handling Pregnancy: Because pregnancy events – particularly the third trimester – can have significant effects on glycemic control, we will ignore any HbA1c measures that occur during a pregnancy period, defined as 9 months before and 3 months after any code indicating a full-term delivery, pre-term delivery, miscarriage, or abortion procedure. We will also ignore any HbA1c measurements that occur during an inpatient hospitalization or during a treatment episode for oral steroid medications. We will also ignore diabetes medication use 9 months before and 3 months after any code indicating a full-term delivery, pre-term delivery, miscarriage, or abortion procedure.

Given the nature of the date ranges for the CDM data, we will not likely be able to construct a meaningful measure of Diabetes Duration at the time of surgery.

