### B. AIM 2 (IMPROVEMENTS IN DIABETES RISK)

To what extent do these bariatric procedures differ on improvements in diabetes risk at 1, 3, and 5 years?

Primary Analysis: Complete three pairwise comparisons (RYGB vs. AGB; RYGB vs. SG; AGB vs. SG) for our primary and secondary outcomes and all sensitivity/heterogeneity analyses on adults  $\geq 20$  years of age using *individual-level data with multiple imputation for missing weight data after surgery*

Secondary Analysis: Complete three pairwise comparisons for our primary and secondary outcomes and all sensitivity/heterogeneity analyses using *distributed data analysis approach*

Primary Outcomes: 1) Rate of diabetes remission (HbA1c  $<6.5\%$  off diabetes medications  $\geq 90$  days);

Secondary Outcomes: 1) Rate of relapse of diabetes after initial remission (restart of medication or HbA1c  $\geq 6.5\%$ ), and 2) Change in HbA1c at 1, 3, and 5 years;

Sensitivity Analyses (for primary outcome): 1) Calendar Year analysis: look at the effects of these procedures on diabetes remission by calendar year

Heterogeneity Analyses (for primary outcome): 1) Complete all analyses on adolescents  $\leq 20$  years of age; 2) Compare individuals with poorly controlled diabetes (HbA1c  $\geq 7\%$ ) vs. controlled diabetes at baseline, 3) Compare insulin use vs. no insulin at baseline; 4) Compare comorbidity groups or comorbidity index score quartiles; 5) Compare baseline BMI ( $\geq 50$  vs  $<50$  kg/m $^2$ ), 6) Compare race/ethnicity (e.g., non-Hispanic black, Hispanic, non-Hispanic white), 7) Compare adults  $<65$  years and 65+ years; 8) Gender (male vs. female).

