### C. ADDITIONAL AIM 2 INCLUSION CRITERIA

For these analyses, eligible patients must have uncontrolled or medication-controlled diabetes at the time of surgery.

1. Hemoglobin A1c (HbA1c)  $\geq 6.5\%$  at the most recent measurement prior to surgery, or
2. Current prescription for diabetes medication at the time of surgery with the most recent HbA1c  $< 6.5\%$ 
  - a. An Insulin and Oral Diabetes Medications List can be found below in Table 4.

Note that Patients taking only metformin will be excluded unless they also have an ICD-9 code for Diabetes (250.x) or have HbA1c  $\geq 6.5\%$  in the year prior to surgery. This includes patients with polycystic ovarian syndrome (PCOS) [2/26/16].

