
	bariatric population to guide possible future studies. Key variables include: PRO item, PRO date, PRO response, PRO method, and PRO mode	
PRESCRIBING	This data table includes information on provider orders for medication dispensing or administration. It will be used to capture the use of diabetes drug treatments, and may be used to identify other comorbid health conditions and/or important co-occurring treatments, such as 2nd generation antipsychotics and obesity drugs, which can have an important impact on body weight. Key variables include: Rx med name, Rx order date, Rx quantity, Rx refills, RxNORM (drug identifier), Rx days supply, Rx frequency, Rx basis (dispensed or administered)	2004 – 2016
DEATH	This table contains reported mortality for patients in the study. This is critical information for Aim 3. Key variables include: death date, death date impute, death source, death match confidence	2004 – 2016
DEATH_CAUSE	This table contains cause of death information for patients in the study. This information will be used for Aim 3. Key variables include: Death cause, code, type, source, and confidence	2004 – 2016
HARVEST	This table identifies attributes associated with each site's specific PCORnet data mart implementation, which will be helpful for data quality checks. Key variables include: data mart ID, name, platform, CDM version, claims use, EHR use, management variables (indicate where imputation or obfuscation were used for variable creation), refresh date (when data were most recently loaded)	NA

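### Aim 2 ignores HbA1c measured during inpatient stays but not diabetes drugs administered in those stays, so a temporary inpatient insulin order can delay remission, count as relapse and distort baseline insulin use

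*SAP*

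**What the plan says.** All references are to the SAP.

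- **HbA1c exclusions** (Analytic Plans by Aim, B. Aim 2, Primary analysis, pregnancy paragraph). Values in the pregnancy window are dropped, and then: "We will also ignore any HbA1c measurements that occur during an inpatient hospitalization or during a treatment episode for oral steroid medications".
- **Drug exclusions** (same paragraph). Only the pregnancy window is covered: "We will also ignore diabetes medication use 9 months before and 3 months after any code indicating a full-term delivery", with the other pregnancy outcomes listed after it.
- **Remission** (same section). An HbA1c below 6.5% after "90+ days of not having any active anti-hyperglycemic prescription order or dispensing post-surgery".
- **Relapse** (Synopsis, B. Aim 2; repeated in Table 5). "Rate of relapse of diabetes after initial remission (restart of medication or HbA1c" of 6.5% or more).
- **Eligibility on drugs** (Additional Aim 2 Inclusion Criteria, item 2). "Current prescription for diabetes medication at the time of surgery with the most recent HbA1c" below 6.5%. The lead sentence of that section requires diabetes at the time of surgery. A note adds that "Patients taking only metformin will be excluded unless they also have an ICD-9 code for Diabetes (250.x") or have a raised HbA1c in the prior year.
- **Source of drug data** (Table 1, PRESCRIBING). "This data table includes information on provider orders for medication dispensing or administration", and "It will be used to capture the use of diabetes drug treatments". The listed variables include Rx basis, which separates dispensed from administered. DISPENSING covers outpatient pharmacy only.
- **Baseline use** (Table 6). Insulin use, oral drug use and number of oral drugs come from the same two tables. The Synopsis also lists insulin versus no insulin at baseline as a subgroup.

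**The concern.** The remission and relapse definitions each have a laboratory half and a drug half. For pregnancy the SAP removes both. For inpatient stays it removes only the laboratory half. Because the drug source includes orders for administration and the remission rule refers to any active order, a programmer following the text would count insulin given for a few days on a ward in the same way as outpatient treatment.

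Remission is the primary outcome of Aim 2 and relapse is a secondary one; both are used again in Aims 4 to 6. The resulting error is tied to being hospitalised after surgery. Aim 3 compares rehospitalisation between procedures. If it differs, the procedure with more readmissions will show later remission and more relapse for reasons unrelated to diabetes. Adjustment for baseline covariates or propensity scores cannot remove this, because the hospital stays occur after baseline.

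**Working it through.** The SAP states no figure on this point, so there is nothing to reproduce. The check sets the rules side by side, then does date arithmetic and one illustration.

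**Which periods are ignored**

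| Period | HbA1c ignored | Diabetes drugs ignored |
|---|---|---|
| Pregnancy window | yes | yes |
| Inpatient stay | yes | no |
| Oral steroid episode | yes | no |

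No other section restricts diabetes drugs to outpatient or dispensed orders. Rx basis is listed in Table 1, but no rule uses it. Since DISPENSING is outpatient, the inpatient route runs through PRESCRIBING.

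**Effect on the 90-day rule**

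Take a patient without diabetes drugs since surgery. The earliest possible remission is about day 90. Suppose a temporary order of length L days starts on day s, before remission has been recorded. The earliest date then becomes s + L + 90. L and s below are assumptions.

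- Index stay, s = 0, L = 3: 0 + 3 + 90 = day 93, a shift of about 3 days.
- Readmission, s = 60, L = 3: 60 + 3 + 90 = day 153, a shift of about 63 days.
- Order starting after day 90, L = 1 to 14: values over L + 90 = 91 to 104 days cannot qualify, which is 91/365 = 25% to 104/365 = 28% of a one-year horizon.
- Order after about day 365 − 90 = 275 in a patient not yet in remission: remission within one year is no longer possible. The 3- and 5-year horizons remain open.

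**Effect on relapse**

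In a patient already in remission, a single order meets the drug half of the relapse definition at once. No duration or setting is required.

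**Effect on baseline insulin**

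The SAP does not define a current prescription, nor whether the index stay belongs to baseline. If it does, perioperative insulin marks a patient as an insulin user, both in the covariate and in the insulin subgroup.

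**Illustration of differential relapse** (all inputs assumed, none from the SAP)

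True relapse is 8 per 100 person-years in both groups, rehospitalisation is 12 versus 8 per 100 person-years, insulin is ordered in a fraction q of stays, and every such order is a false relapse.

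Apparent ratio = (0.08 + 0.12q) / (0.08 + 0.08q)

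- q = 0.1: 0.092 / 0.088 = 1.05
- q = 0.2: 0.104 / 0.096 = 1.08
- q = 0.3: 0.116 / 0.104 = 1.12

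The true ratio is 1.00 throughout. With equal rehospitalisation the ratio stays at 1.00 and only the relapse level is inflated.

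**The case against.** The SAP never states that hospital-administered drugs count; it is silent. Prescription and restart can be read as ongoing treatment, Table 1 already lists the field needed to separate the orders, and the Plan for Data Queries leaves coding detail to specifications not shown here. The point about silence stands. It does not settle the matter: the remission rule speaks of any active order, the named source includes orders for administration, and the same paragraph shows that the authors knew how to exclude drug use when they meant to.

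Four stronger readings are tempting and are not supported.

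- *Non-diabetic patients enter Aim 2 through perioperative insulin.* A reader might infer this from item 2 of the inclusion criteria, since the diagnosis-code safeguard covers metformin only. The section's lead sentence requires diabetes at surgery, so this route is secondary. It depends on a program applying item 2 without that sentence.
- *Inpatient insulin blocks remission.* Usually it delays it. For the index stay the delay is a matter of days.
- *The same rule must apply to drugs started during oral steroids.* The SAP gives a reason for its exclusions only for pregnancy. An unreliable laboratory value and a newly started drug are different things, and a drug started on steroids may reflect true relapse. Whether to discount it is a debatable definition, not an error.
- *The bias has a known size.* All the rates above are assumed. Some inpatient orders will reflect true relapse, so counting every one as false puts the illustration at the high end for its inputs.

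**Conclusion.** The concern holds for inpatient administered drugs. Followed as written, Aim 2 can count a temporary inpatient insulin order against remission, as relapse and as baseline insulin use, although it discards the HbA1c taken in the same stay. For remission the cost is a delay until 90 days after the order ends, with loss of the outcome only when no qualifying HbA1c follows within the 1-, 3- or 5-year horizon. For relapse one order can suffice.

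Bias between procedures requires that post-surgical hospitalisation differ by procedure and that insulin orders in those stays reach the PRESCRIBING table. The documents show that the second is possible and that the first is a study question; they give no rates for either. The illustrative 1.05 to 1.12 for relapse shows the direction and a plausible order of size under the stated assumptions, and is not an estimate for this study. The gap deserves correction because it touches the primary outcome and is cheap to close.

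**What to change.** Add to the Aim 2 primary analysis, next to the HbA1c exclusions:

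> Diabetes medication orders with Rx basis recorded as administered (or, where Rx basis is missing, orders that start and end within an inpatient stay, including the index stay) will not count toward Aim 2 eligibility, baseline insulin use, the 90-day off-medication period or relapse. Discharge prescriptions and outpatient orders or dispensings will count.

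The second sentence is needed. Dropping every order linked to an inpatient encounter would discard discharge prescriptions and could score treated patients as drug-free. DISPENSING could not reliably recover them, since Table 1 says not all sites have it.

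Any rule for drugs started during oral steroid episodes, including a pause of the 90-day period, should stay out of the main definition or be run only as a sensitivity analysis.

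The cost is SAP wording and a filter on a field already in Table 1, with no new data. The downside is small: sites with incomplete Rx basis need the fallback. Table 1 lists no encounter link for PRESCRIBING, so this means matching order date and days supply to the admission and discharge dates in ENCOUNTER.

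### Aim 2 ignores diabetes drug use around pregnancy without stopping the 90-day off-drug clock, so some recently treated women can be scored as in remission

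*SAP*

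**What the plan says.** All of the rules stand in the SAP under Analytic Plans by Aim, B. Aim 2, Primary analysis.

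- Remission, the primary outcome, is "defined as HbA1c <6.5% after 90+ days of not having any active anti-hyperglycemic prescription order or dispensing post-surgery". The team will "fit a Cox proportional hazards model to estimate the effects of surgery on diabetes remission", with follow-up capped at 1, 3 or 5 years.
- Under Handling Pregnancy, laboratory values are dropped: "we will ignore any HbA1c measures that occur during a pregnancy period, defined as 9 months before and 3 months after any code". The window is opened by "any code indicating a full-term delivery, pre-term delivery, miscarriage, or abortion procedure".
- Drug records get the same window: "We will also ignore diabetes medication use 9 months before and 3 months after any code" of that kind.

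The synopsis for Aim 2 and Table 5 add a secondary outcome that also depends on drug records: "Rate of relapse of diabetes after initial remission (restart of medication or HbA1c" at or above 6.5%).

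The SAP does not say whether ignored medication time counts as off-drug time, pauses the 90-day count, restarts it, or is censored. Table 5 repeats the remission definition in shorter form and does not fill the gap.

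**The concern.** Ignoring an HbA1c value and ignoring a drug record look symmetrical but are not. An ignored HbA1c cannot trigger anything. An ignored drug record can, because remission is met partly by the absence of drug records. Dropping true exposure therefore creates apparent non-exposure.

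The outcome affected is the primary one for Aim 2. In a time-to-first-event analysis a false remission ends the patient's time at risk. It also places her in the set at risk of relapse, where her next counted prescription may be scored as a relapse from a remission she never had. Aims 4 to 6 reuse both outcomes.

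**Working it through.** The SAP gives no figure to reproduce here, so the check is a day count on the stated rules.

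**Inputs.** Day 0 is the pregnancy code. One month is 365.25 / 12 = 30.44 days. Nine months is 9 × 30.44 = 274 days and three months is 3 × 30.44 = 91 days, so the window runs from day −274 to day +91. That is about 365 days, or 365 / 90 = 4.1 times the off-drug requirement. The part after the code (days 1 to 91) is by itself long enough to satisfy the 90-day rule.

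**Formulas.** Let L be the last day of drug use and t the day of an HbA1c below 6.5%.

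- True off-drug run = (t − 1) − L.
- Counted run when in-window use is dropped and the woman was treated up to the window's opening: the last counted drug day is −275, so the run is (t − 1) + 275 = t + 274.
- Run if the count starts at the end of the window: (t − 1) − 91.

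The cases assume surgery before day −274 and, except in the last row, no counted drug after day 91.

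| Case | True run | Counted run, use dropped | Scored as remission? | Meets the 90-day definition? | Run counted from window end |
|---|---|---|---|---|---|
| Treated to day 91, tested day 92 | 91 − 91 = 0 | 366 | Yes | No | 0 |
| Treated to day 60, tested day 92 | 91 − 60 = 31 | 366 | Yes | No | 0 |
| Treated to day 91, tested day 151 | 150 − 91 = 59 | 425 | Yes | No | 59 |
| Treated to day 91, tested day 182 | 181 − 91 = 90 | 456 | Yes | Yes | 90 |
| Treated to day 0, tested day 92 | 91 − 0 = 91 | 366 | Yes | Yes | 0 |
| Treated throughout, tested day 30 | 0 | HbA1c ignored | No | No | not applicable |
| Treatment recorded past the window, tested day 120 | 0 | 0 | No | No | 0 |

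**Where the error can occur.** A test inside the window is ignored, so the first eligible test day is 92. A false remission needs (t − 1) − L ≤ 89. With L at most 91, t is at most 181. The exposed test days are 92 to 181, which is 181 − 92 + 1 = 90 days. At t = 92 the women at risk are those whose last drug use fell between day 2 and day 91.

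**Pausing versus restarting.** A pause that carries pre-window credit forward does not fully remove the error. Take a woman off drug for the 60 days before the window, treated inside it to day 91, and tested on day 122. Her paused count is 60 + (121 − 91) = 90, which qualifies. Her true run is 30.

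**The case against.** The strongest reply is that *ignore* need not mean *treat as untreated*. If the team meant the window as unobserved time with a fresh count afterwards, no error arises, and the section on data queries leaves functional and technical specifications to be written later. That is fair as far as it goes. But the same section makes the scientific teams responsible for defining outcomes in the analytic plan, and the plan uses the same word for HbA1c, where it plainly means that the record is dropped. A programmer following the text would have no instruction to stop the count.

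Four stronger readings are tempting and are not supported.

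- *Women treated throughout pregnancy are generally counted as in remission.* They are not. HbA1c inside the window cannot trigger remission, and a counted active drug after the window resets the count.
- *A 90-day fill on day 60 followed by a test on day 92 gives a false remission.* That supply runs to about day 150 and is active on day 92. The SAP ignores use inside the window; it does not say that later supply from the same fill is erased. The example works only if the whole fill is dropped. The text does not exclude that coding, which is one more reason to settle it.
- *The share of patients misclassified equals the pregnancy rate.* The SAP gives no such rate, and it would only be an upper limit. An error also needs no earlier remission, recent drug use inside the window, no counted drug afterwards, and a low HbA1c in the exposed 90 days.
- *The sex and age subgroup results are distorted.* The errors do fall only on patients with pregnancy codes. But those analyses compare procedure effects, the adult age split is at 65, and the SAP shows no mechanism making the error differ by procedure. Table 6 says that procedure choice varies with age and may vary with sex, so equal error across procedures is not guaranteed either. The direction and size are unknown.

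**Conclusion.** The point holds in a limited form. Read literally, the pregnancy rule lets the Aim 2 primary outcome be met by women with fewer than 90 true off-drug days: 31 days for treatment to day 60 and a test on day 92, and 59 days for treatment to day 91 and a test on day 151. These women also enter the relapse analysis wrongly.

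The conclusion rests on ignored use being dropped while the count runs on, and on no counted active drug after the window. The number affected and the bias in the hazard ratio cannot be computed from the SAP. Because several conditions must coincide, the effect on the overall hazard ratio is probably small. The rule should still be corrected, since it conflicts with the SAP's own definition of a primary outcome and is cheap to repair.

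**What to change.** Add a short derivation rule to Handling Pregnancy under Aim 2:

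- The pregnancy window is unobserved time for the remission derivation, and ignored medication time never counts as off-drug time.
- The 90-day off-drug count starts at the end of the window. This is simpler than a pause and, unlike a pause, does not carry off-drug days across unobserved treatment.
- Any order or dispensing whose supply extends past the window counts as active after it, for as long as the supply lasts.

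This is a data-handling definition and changes no clinical rule.

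The programming cost is small, but the rule delays some genuine remissions. A woman off drug since delivery truly qualifies on day 92; under this rule she qualifies on day 182 at the earliest, which is 182 − 92 = 90 days later, and then only at her first low HbA1c from that day on. Women off drug before, during and after pregnancy are delayed in the same way if not already in remission. A few such remissions may fall beyond a 1-, 3- or 5-year limit and be lost to that analysis. Reporting how many patients have a window overlapping their time at risk would show whether either error matters.
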